2.4 RANDOMIZATION

Subjects are to be implanted with the same IOL in both eyes, the ZFR00 IOL, the ZYR00 IOL or the ZLB00 control IOL, according to a randomization schedule. JJV will use a centralized electronic randomization system.

If a surgeon implants the wrong study lens, i.e., other than the one on the randomization schedule, the subject's study data will be analyzed according to the actual lens received; however, the number of these events will be reported.

3 ACCOUNTABILITY/DEMOGRAPHICS

3.1 ACCOUNTABILITY

The number of enrolled subjects will be tabulated by site for first and second eyes. Subject accountability will be summarized as a frequency distribution by scheduled visits. A frequency table by IOL will be generated, showing the number of available eyes (those in interval and outside of the interval) and the number of missing (e.g., discontinued, missed visit, etc.) and active subjects.

4 OPERATIVE PARAMETERS

Operative parameters related to surgical complications or procedures for first and second eyes will be reported for each IOL model. The frequency and proportion of eyes with selected responses will be tabulated. Statistical comparisons between IOL groups will be performed as described above for demographic data. Two-sided testing with an alpha level of 0.05 will be used for these operative parameters.

6 POSTOPERATIVE ANALYSES - PRIMARY SAFETY ENDPOINTS

6.1 MODEL ZFR00: RATES OF ADVERSE EVENTS VS. ISO SPE RATES

The primary Model ZFR00 safety endpoint for this study is the rate of adverse events vs. ISO SPE rates at 1 month postoperative. The frequency and proportion of first eyes and second eyes with these events will be reported over time by IOL group. Statistical comparisons to ISO SPE rates will be based on first-eye data; adverse event rates for Model ZFR00 lens first eyes will be compared to the ISO SPE rates using a one-sided, exact test based on the binomial distribution. The null hypothesis is that the AE rate for Model ZFR00 investigational lens eyes is lower than or equal to the ISO SPE values, and the alternative hypothesis is that the AE rate for study eyes is higher than the ISO SPE values.

 $\begin{array}{l} H_o: \ p_t \leq \ p_i \\ H_1: \ p_t > p_i \end{array}$

where

 p_t = proportion of Model ZFR00 investigational lens eyes with the AE p_i = proportion of eyes reported in ISO SPE rates with the AE

Reject the null hypothesis if one-sided p-value < 0.05.

6.2 MODEL ZYR00: RATES OF ADVERSE EVENTS VS. ISO SPE RATES

The primary Model ZYR00 safety endpoint for this study is the rate of adverse events vs. ISO SPE rates at 1 month. The frequency and proportion of first eyes and second eyes with these events will be reported over time by IOL group. Statistical comparisons to ISO SPE rates will be based on first-eye data; adverse event rates for Model ZYR00 lens first eyes will be compared to the ISO SPE rates using a one-sided, exact test based on the binomial distribution. The null hypothesis is that the AE rate for Model ZYR00 investigational lens eyes is lower than or equal to the ISO SPE values, and the alternative hypothesis is that the AE rate for study eyes is higher than the ISO SPE values.

 $H_o: p_t \le p_i$ $H_1: p_t > p_i$ where

pt = proportion of Model ZYR00 investigational lens eyes with the AE
pi = proportion of eyes reported in ISO SPE rates with the AE
Reject the null hypothesis if one-sided p-value < 0.05.

7 POSTOPERATIVE ANALYSIS: OTHER ENDPOINTS

7.1 OTHER INTERMEDIATE VISUAL ACUITY ENDPOINTS

For binocular UCIVA and DCIVA and monocular UCIVA, a superiority approach similar to DCIVA described above will be used.

In addition, the frequency and proportion achieving each line for all other intermediate endpoints will be reported over time by IOL group.

7.3 DEFOCUS

Best-corrected distance defocus testing will be performed at the 1- and 6-month visits (monocular at 1 month and binocular at 6 months). The mean visual acuity at each diopter will be plotted. The defocus curve will be presented for monocular and binocular by IOL model. The diopters of defocus where the mean visual acuity of 20/32 or better is achieved will be derived by visual inspection of the defocus curve. In addition, defocus curves will also be stratified by pupil size (≤ 2.5 mm, > 2.5 mm to < 4.0 mm, and ≥ 4.0 mm) for each IOL model. For binocular defocus curve, the average of the two pupil sizes will be used for stratification.

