**EVALUATION CRITERIA:**

The purpose of this clinical study is to evaluate the safety and effectiveness of the next-generation TECNIS IOLs. The primary effectiveness endpoint is mean monocular distance corrected intermediate visual acuity under photopic conditions at 66 cm. Other effectiveness endpoints include mean monocular and binocular diopters of defocus, monocular and binocular uncorrected and best corrected distance, uncorrected intermediate, uncorrected near and distance corrected near, monocular and binocular 10% low-contrast distance corrected visual acuities, and questionnaire responses.

The primary safety endpoint is adverse event rates versus ISO 11979-7:2006/ Amd.1:2012(E) Safety and Performance Endpoint (SPE) rates. Additional safety endpoints include the proportion of first-implanted eyes achieving 20/40 or better monocular photopic best corrected distance visual acuity vs. the ISO SPE rate, optical/visual symptoms, medical/lens findings, binocular best corrected distance contrast sensitivity and visual symptoms via PRO instrument.

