### 6.3 OTHER ENDPOINTS

- Monocular and binocular, best corrected distance depth of focus
- Monocular BCDVA percent 20/40 or better vs. ISO SPE rate
- Binocular UCDVA, BCDVA, UCIVA, DCIVA, UCNVA and DCNVA
- Monocular UCDVA, UCIVA, UCNVA and DCNVA
- Monocular and binocular low-contrast BCDVA (10%)
- Monocular and binocular best corrected distance contrast sensitivity vs control (mesopic with and without glare at 1.5, 3, 6, and 12 cpd, photopic without glare at 3, 6, 12, and 18 cpd)
- Visual symptoms via PRO instrument
- Ocular/visual symptoms (non-directed responses as obtained from the open-ended question "Are you having any difficulties with your eyes or vision?")
- Subject spectacle independence and satisfaction questionnaire responses
- Medical findings/complications
- Lens findings/complications

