#### DEPTH OF FOCUS TESTING (MASKED PROCEDURE)

Monocular, best corrected distance depth of focus testing will be performed at the 1-month visit on the first eye only for all subjects, and binocular best corrected distance depth of focus testing will be performed at the 6-month visit on all subjects.

Depth of focus testing will be performed under photopic conditions (85 cd/m^2, 80-110 cd/m^2 acceptable) using the M&S System at 4.0 meters with the ETDRS refraction in place (no adjustment necessary for test distance). The subject is to be defocused in -0.50 D increments with spherical minus lenses; at each defocus increment, a LogMAR measurement is obtained. Testing is to be conducted from +2.00 D through -4.00 D of defocus. Further instructions for defocus testing are detailed in **Appendix I**.

The following defocus curve measurements are to be performed per the visit schedule in **Appendix A**:

Test	Test Distance	Illumination	Type of Testing	Refraction Adjustment
Monocular Depth of Focus	4 m	Photopic (85 cd/m  )	Monocular	No adjustment; ETDRS Rx only
Binocular Depth of Focus	4 m	Photopic (85 cd/m  )	Binocular	No adjustment; ETDRS Rx only

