### **Defocus Endpoints**

For defocus results, the defocus curve will be produced by IOL group. The diopters of defocus where the mean visual acuity 20/32 or better is achieved will be derived by visual inspection of the defocus curve.

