1 INTRODUCTION

This document summarizes the statistical methods to be implemented during the analysis of data for the TECNIS[®] Next-Generation IOLs, Models ZFR00 and ZYR00, clinical study (Protocol SUR-CAT-652-1001). This study will be a prospective, multicenter, subject/evaluator-masked, bilateral, randomized, clinical trial conducted at up to 14 sites. The two test lenses, TECNIS Model ZFR00 and Model ZYR00 IOLs, will be compared to the control lens, TECNIS Multifocal IOL, Model ZLB00, separately. Subjects are to be implanted with the same IOL in both eyes, the ZFR00 IOL, the ZYR00 IOL or the multifocal control IOL. Up to 260 subjects will be enrolled to achieve approximately 220 randomized and bilaterally-implanted subjects, resulting in approximately 195 evaluable subjects (65 in each IOL group) at 1 and 6 months.

The primary effectiveness endpoints for this study are mean (LogMAR) monocular, photopic, distance corrected intermediate visual acuity (DCIVA) at 66 cm. The primary safety endpoints are adverse event rates versus ISO 11979-7:2006/ Amd.1:2012(E) Safety and Performance Endpoint (SPE)¹ rates.

Other effectiveness endpoints include mean monocular and binocular diopters of defocus, monocular and binocular uncorrected and best corrected distance, uncorrected intermediate, uncorrected and distance corrected near, monocular and binocular 10% low-contrast distance corrected visual acuities, and questionnaire responses.

Additional safety endpoints include the proportion of first implanted eyes achieving 20/40 or better monocular photopic best corrected distance visual acuity vs. the ISO SPE rate, optical/visual symptoms, medical/lens findings, monocular and binocular best corrected distance contrast sensitivity and visual symptoms via PRO instrument.

The key study timeframe will be the 1-month postoperative visit, although data will be reviewed at other time points as well.

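### Diopters of defocus is read by eye from each lens group's mean curve, so it has no calculation rule, no confidence interval and no specified comparison with control

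*SAP*

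**What the plan says.** SAP 1 states: "Other effectiveness endpoints include mean monocular and binocular diopters of defocus". The protocol synopsis lists the same endpoint under Evaluation Criteria. Protocol 6.3 lists it as "Monocular and binocular, best corrected distance depth of focus".

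The derivation is the same in both documents. SAP 7.3 states: "The mean visual acuity at each diopter will be plotted". Protocol 20.3 defines the quantity as "The diopters of defocus where the mean visual acuity 20/32 or better is achieved", and both documents say that it "will be derived by visual inspection of the defocus curve". On the number of curves, SAP 7.3 adds: "The defocus curve will be presented for monocular and binocular by IOL model". Curves within three pupil-size strata are also planned.

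The data behind the curves are individual. Protocol 10.7 says that "at each defocus increment, a LogMAR measurement is obtained", in 0.50 D steps from +2.00 D to -4.00 D, which is 13 levels. Appendix I of the protocol has the letters correct recorded in the data capture system at every level.

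The defocus rows of SAP Appendix I list curves only, whereas the acuity and contrast sensitivity rows list N, mean, SD and a confidence interval. Protocol 20 commits to comparing each test lens with the control in all analyses, but no method is given for defocus.

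**The concern.** An endpoint named as a mean in diopters is produced by looking at a graph. Four things are left open:

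- **Where the curve crosses.** Acuity is known only every 0.50 D. Two readers may place the crossing at different points within a step, and no interpolation rule settles it.
- **What counts.** If the mean curve falls below 20/32 at an intermediate distance and recovers, the plan does not say whether the range ends at the first crossing or whether later segments are added. Nor does it say what to do with a curve still at 20/32 or better at -4.00 D.
- **Uncertainty.** A reading by eye yields no standard error or confidence interval.
- **Comparison.** No contrast with the control is defined.

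Protocol 4 says that the study is to help select a final design from two candidates. Table 1 of the protocol already uses a range in diopters as a product descriptor: through 2.0 D for the parent lens, Model ZXR00, and through 3.0 D for the test lenses. A figure used in that way should be reproducible and show its precision.

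**Working it through.** The documents give no SD, margin, power or expected value for defocus, so there is no stated figure to reproduce. Curve shapes and SDs below are assumptions unless a source is named.

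**1. Threshold.** SAP Appendix II converts 0.20 LogMAR to 20 × 10^0.20 = 31.7, that is 20/32. The crossing is therefore at 0.20 LogMAR.

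**2. Size of the undefined counting rule.** Take an assumed mean curve on the near side, with x in diopters: -0.02 + 0.25·exp(-((x-1)/0.5)²) + 0.30·max(x-2.5, 0).

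- The values at x = 0.5, 1.0 and 1.5 are 0.072, 0.230 and 0.072. At x = 3.0 and 3.5 they are 0.130 and 0.280.
- First crossing: 0.5 + 0.5 × (0.200 - 0.072)/(0.230 - 0.072) = 0.905 D.
- By symmetry the curve is back at 0.20 at 1.095 D. It leaves again at 3.0 + 0.5 × (0.200 - 0.130)/(0.280 - 0.130) = 3.233 D.
- Continuous from 0 D: **0.91 D**. All qualifying segments: 0.905 + (3.233 - 1.095) = **3.04 D**.

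The same curve gives two answers about 2.1 D apart. In simulations of 10,000 subjects with this shape they were 0.90-0.91 D and 3.03-3.05 D.

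**3. Size of the missing uncertainty.** For the crossing of a mean curve, the standard error is approximately (acuity SD/√n)/slope at the crossing. Use n = 65 per group (SAP 1) and acuity SDs of 0.08 to 0.16 LogMAR; the upper value is the 1.6 lines that Protocol 20.6 assumes for the primary endpoint. Slopes are assumed. Half-width per lens = 1.96 × SD/(√65 × slope); for a lens difference, multiply by √2.

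| Slope (LogMAR/D) | SD (LogMAR) | 95% half-width, one lens | 95% half-width, difference |
|---|---|---|---|
| 0.15 | 0.08 | 0.13 D | 0.18 D |
| 0.15 | 0.16 | 0.26 D | 0.37 D |
| 0.08 | 0.08 | 0.24 D | 0.34 D |
| 0.08 | 0.16 | 0.49 D | 0.69 D |

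A one-step difference of 0.50 D between lenses would be outside sampling error in the first three rows and inside it in the last. The planned output would not tell the reader which applies.

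**4. Is the mean-curve range biased?** Simulated comparison of the mean curve's crossing with the average of individual crossings, at between-subject acuity SDs of 0.08 to 0.16 LogMAR:

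| Assumed shape | Mean curve | Mean of subjects (continuous from 0 D) |
|---|---|---|
| Parallel straight lines, 0.15/D | 1.66-1.67 D | 1.66-1.69 D |
| Slopes varying between subjects | 1.54-1.55 D | 1.75-1.80 D |
| Accelerating curve | 2.87-2.88 D | 2.68-2.84 D |
| Shallow slope, cut off at 4 D | 3.10-3.14 D | 2.75-3.03 D |
| Dip 0.15, mean stays within threshold | 3.23-3.24 D | 2.51-2.84 D |
| Dip of varying position | 3.23-3.24 D | 2.27-2.33 D |
| Dip 0.25, mean fails threshold | 0.90-0.91 D | 1.74-1.87 D |

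The difference is nil, negative or positive, according to the shape.

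**5. Is the per-subject range a sound yardstick?** Give every subject the same true curve and add only test noise of SD 0.06 LogMAR. A continuous-from-0 D range stops at the first bad reading, so noise alone shortens it. In one such check a true 3.25 D range averaged 2.4 D. With the curve in step 2 and its dip coefficient reduced to 0.15, 0.17 or 0.19, the true range is 3.23 D and the subject averages were 2.94, 2.74 and 2.48 D, while the mean curve still gave 3.23 D.

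**The case against.** The strongest reply is that little depends on this figure. The protocol synopsis states: "The primary effectiveness endpoint is mean monocular distance corrected intermediate visual acuity under photopic conditions at 66 cm". Defocus has no hypothesis, power statement or success criterion, and no document gives a design-selection rule based on it. Differences across the range are tested on subject-level data elsewhere: superiority at 66 cm (1/0.66 = 1.5 D), and non-inferiority at 40 cm (1/0.40 = 2.5 D) and at distance. Protocol and SAP agree on the derivation, and general conventions call for N, mean and SD for continuous variables. All of this stands and limits the importance of the point. It does not supply a rule, an interval or a comparison for the diopter figure, and the planned defocus rows show curves only.

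A reader might infer three stronger things that the documents do not support:

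- **That the reported range is overstated.** No curve shape or defocus SD is given. Over assumed shapes the sign changes, and part of any apparent excess over a per-subject continuous range is test noise shortening the latter.
- **That the trial's central design aim goes untested.** Protocol 7.1 states the depth-of-focus aim relative to the parent lens, Model ZXR00, which is not an arm. Against the multifocal lens the aim is better intermediate acuity, which the primary endpoint tests.
- **That subject-level data are missing.** Letter scores are collected at every step; only a defined calculation is absent.

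**Conclusion.** The point holds as a matter of analysis method for an other effectiveness endpoint. Following the plan gives, for each lens, a monocular and a binocular figure that depend on the reader within a 0.50 D step, have no standard error or confidence interval, and have no specified comparison with the control, although the data for all three are collected. Calling the result a mean of diopters is also loose, since acuity is averaged first.

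The size is known only under assumptions: about ±0.18 to ±0.69 D of unreported uncertainty on a lens difference, for acuity SDs of 0.08 to 0.16 LogMAR and slopes of 0.08 to 0.15 LogMAR/D, and about 2.1 D between counting rules if a mean curve dips past the threshold as in the example. The direction of any bias is not established. No success criterion changes.

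**What to change.** In SAP 7.3, Protocol 20.3 and the defocus rows of SAP Appendix I:

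1. Replace visual inspection with a calculated range on each lens's mean curve, using linear interpolation at 0.20 LogMAR between 0.50 D steps.
2. State before analysis whether only the range continuous from 0 D counts or all qualifying segments do, and how a mean curve still at 0.20 LogMAR or better at -4.00 D is reported.
3. Report a 95% confidence interval for each lens and for each test-minus-control difference by bootstrap resampling of subjects within lens group: monocular at 1 month, binocular at 6 months.
4. Report N, mean, SD and confidence interval of acuity at each defocus step, and keep the plotted curves.
5. A per-subject range may be added as supportive only, because test noise shortens a first-crossing measure.

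The cost is a little programming and a few lines of text, with no new testing. The reported range will carry visible uncertainty.

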7.4 CONTRAST SENSITIVITY

Contrast sensitivity testing will be performed at the 1- and 6-month visits (monocular at 1 month and binocular at 6 months). The contrast sensitivity score will be converted to log units prior to analysis (see conversion formula in Appendix II). The average of the two contrast sensitivity log scores will be used for the analysis. Analyses including mean, standard deviation, median, minimum, maximum and 90% confidence intervals will be presented by IOL group.

In addition, contrast sensitivity will also be stratified by pupil size (photopic condition using photopic pupil size ≤ 2.5 mm, > 2.5 mm to < 4.0 mm, and ≥ 4.0 mm; mesopic condition using mesopic pupil size ≤ 4.0 mm, > 4.0 mm to < 5.0 mm, and ≥ 5.0 mm) for each IOL model. For binocular testing, the average of the two pupil sizes will be used for stratification.

7.5 MANIFEST REFRACTION

Descriptive analysis of refractive sphere, cylinder and spherical equivalent (MRSE) will be reported by IOL groups for both eyes. Since refraction was performed at 4M, 0.25D will be subtracted from the sphere value. Refractive data will then be converted to plus cylinder notation.

MRSE is then calculated by the following formula: MRSE = sphere + $\frac{1}{2}$ cylinder.

7.6 MEDICAL AND LENS FINDINGS

Rates of postoperative medical and lens findings will be tabulated with the frequency and proportion of eyes with these events reported over time by IOL group. As mentioned above in Section 6.1 and 6.2 Rates of Adverse Events, medical complication rates listed in ISO-11979 will be compared to the ISO SPE rates for test lens first eyes at 6 months using a one-sided, exact test based on the binomial distribution. The null hypothesis is that the study rate for test lens eyes is lower than or equal to the ISO rate, and the alternative hypothesis is that the rate for test lens eyes is greater than the ISO rate. For adverse events and other medical and lens findings, data will be reported for first eyes, and data for second eyes will be reported as supportive data.

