## 10.2 VISIT SCHEDULE

The study visit schedule for all study subjects is outlined in **Table 2**.

All subjects are intended to have bilateral cataract surgery with the second-eye surgery occurring after the 1-week exam for the first eye but no more than 30 days after the first-eye surgery. After each surgery, each eye will be examined 1 day postoperatively (1-2 days) and again at 1 week (7-14 days). Following the second-eye surgery, both eyes will be evaluated at 1 month (30-60 days) and 6 months (120-180 days). Unscheduled visits may be conducted as necessary at the discretion of the investigator for medically-indicated follow-up.

TABLE 2: Visit Schedule

VISIT	EYES EVALUATED	EXAM	VISIT WINDOW
1	Both Eyes	Preoperative Exam	Within 60 days prior to 1 st surgery
2	First Eye	Operative	0-60 days after preoperative exam
3	First Eye	1 day	1-2 days postoperative
4	First Eye	1 week a	7-14 days postoperative
5	Second Eye	Operative a	No more than 30 days after 1 st eye surgery
6	Second Eye	1 day	1-2 days postoperative
7	Second Eye	1 week	7-14 days postoperative
8	Both Eyes	1 month b	30-60 days postoperative from 2 nd implant
9	Both Eyes	6 months c	120-180 days postoperative from 2 nd implant

a The 1-week exam for the first eye is to be completed prior to surgery on the second eye.

b If for any reason the second eye does not get implanted, the first eye should be seen for the 1-month study visit 37 - 90 days following the first-eye implant.

c If for any reason the second eye does not get implanted, the first eye should be seen for the 6-month study visit 127 - 210 days following the first-eye implant.

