#### DILATED FUNDUS EXAM

A dilated fundus exam is to be performed at the 6-month visit to evaluate retinal status and fundus visualization.

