### **Study-Specific Serious Anticipated Adverse Events**

The following is a list including, but not limited to, ocular serious adverse events (SAE) that are anticipated and must be reported to JJV for this study. Any events that are unlikely but anticipated (i.e., endophthalmitis) will be reported to the FDA and other appropriate regulatory agencies.

- Endophthalmitis/Intraocular infection
- Hypopyon
- Hyphema
- IOL dislocation
- Cystoid macular edema
- Pupillary block
- Retinal detachment/tear
- Persistent corneal edema
- Persistent iritis
- Persistent uveitis
- Persistent raised IOP requiring treatment
- Toxic anterior segment syndrome
- Visual symptoms requiring secondary surgical intervention (e.g., lens removal)
- Tilt and decentration requiring secondary surgical intervention (e.g., repositioning)
- Residual refractive error resulting in a secondary surgical intervention
- Retained lens material resulting in secondary surgical intervention

**NOTE 1:** Wound burps during the first week postoperatively, suture removal, planned blepharoplasty and Nd:YAG capsulotomy (for PCO) are not considered adverse events for this study.

**NOTE 2:** Raised IOP requiring treatment, corneal edema, and iritis will only be considered serious if persistent at the final study visit (120-180 days postoperative) or sight-threatening at the time of occurrence. Treatment merely to hasten the resolution of such conditions (and not intended to prevent permanent damage to the eye) will not be reported as serious adverse events.

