#### **MODEL ZYR00: RATES OF ADVERSE EVENTS VS. ISO SPE RATES**

The primary Model ZYR00 safety endpoint for this study is the rate of adverse events vs. ISO SPE rates at 1 month postoperative. The frequency and proportion of first and second eyes with these events will be reported over time by IOL group. Statistical comparisons to ISO SPE rates will be based on first-eye data; adverse event rates for Model ZYR00 investigational lens first eyes will be compared to the ISO SPE rates using a one-sided, exact test based on the binomial distribution. The null hypothesis is that the AE rate for Model ZYR00 investigational lens eyes is lower than or equal to the ISO SPE values, and the alternative hypothesis is that the AE rate for study eyes is higher than the ISO SPE values.

$$H_0: p_t \leq p_i$$

$$H_1: p_t > p_i$$

where

$p_t$  = proportion of Model ZYR00 investigational lens eyes with the AE

$p_i$  = proportion of eyes reported in ISO SPE rates with the AE

Reject the null hypothesis if one-sided p-value < 0.05.

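### The primary adverse-event test against ISO rates is dated 1 month, too early for the protocol's persistence rule, and SAP 7.6 attributes a 6-month test to the same sections

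*SAP*

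**What the plan says.** **Primary safety test.** SAP 6.1: "The primary Model ZFR00 safety endpoint for this study is the rate of adverse events vs. ISO SPE rates at 1 month postoperative". SAP 6.2: "The primary Model ZYR00 safety endpoint for this study is the rate of adverse events vs. ISO SPE rates at 1 month". Protocol 20.2 gives the same date for both lenses; for ZYR00 it reads "The primary Model ZYR00 safety endpoint for this study is the rate of adverse events vs. ISO SPE rates at 1 month postoperative". The test uses first eyes and a one-sided exact binomial comparison with the ISO rate at 0.05. Rejection means the lens has a higher rate than the standard.

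**SAP 7.6, under the other endpoints.** The sentence opens "As mentioned above in Section 6.1 and 6.2 Rates of Adverse Events" and goes on to say that "medical complication rates listed in ISO-11979 will be compared to the ISO SPE rates for test lens first eyes at 6 months". The test, its direction, the benchmark and the eyes are those of 6.1 and 6.2. Only the date differs.

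**Event rule.** Protocol 11.1 lists persistent corneal edema, persistent iritis and persistent raised IOP requiring treatment among the anticipated serious events. NOTE 2 adds: "Raised IOP requiring treatment, corneal edema, and iritis will only be considered serious if persistent at the final study visit (120-180 days postoperative"), or if sight-threatening when they occur.

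**Visits.** Protocol 10.2: after the second surgery, "both eyes will be evaluated at 1 month (30-60 days) and 6 months (120-180 days"). Second-eye surgery is at most 30 days after the first.

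**The concern.** One comparison carries two dates, and 7.6 credits its 6-month date to sections that contain no 6-month test. If this were only a slip, deleting a phrase would settle it. But the earlier date, which the plan labels primary, falls before the protocol allows edema, iritis or raised IOP to be called persistent.

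Two things can then go wrong. If the count follows NOTE 2, the primary test has nothing to count in those categories apart from sight-threatening cases, and it cannot flag a lens for them whatever the true rate. If instead any edema or iritis present at 1 month is counted, eyes that recover before day 120 can flag an acceptable lens. In either case the 1-month and 6-month tests can disagree on the same eyes, and the plan does not say how to read such a disagreement. Protocol section 4 says the study is meant to help select a final design from two candidates, so the role of each test is best fixed before data are seen.

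**Working it through.** **Step 1. Calendar for a first eye** (Protocol 10.2, Table 2)
- Second surgery: no later than day 30 after the first.
- 1-month visit: 30-60 days after the second implant. Latest first-eye day = 30 + 60 = 90. Table 2 footnote b gives the same upper limit (37-90 days) for subjects implanted in one eye only.
- NOTE 2 persistence: from day 120.
- Gap: 120 - 90 = at least 30 days. The windows do not overlap.

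**Step 2. What the 1-month test can count**
- Persistent edema, iritis, raised IOP: none under NOTE 2, unless sight-threatening.
- Endophthalmitis, hyphema, hypopyon, lens dislocation and similar events: countable at 1 month.

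The structural zero therefore covers the persistent categories only.

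**Step 3. Sample available.** The plan's figure reproduces: 65 / (1 - 0.10) = 72.2, rounded up to 73 implanted per group. No power is stated for the safety test.

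**Step 4. Exact test.** For k events in n eyes and ISO rate p0,

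p-value = P(X ≥ k) = 1 - Σ(j=0 to k-1) C(n,j) p0^j (1-p0)^(n-j).

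The threshold c is the smallest k with p-value < 0.05. Example with n = 65, p0 = 1%: P(X ≥ 2) = 0.138 and P(X ≥ 3) = 0.028, so c = 3. The chance of flagging the lens is P(X ≥ c) at the true rate. The SPE rates are not in the documents, so p0 is assumed over 0.3% to 3%, and the true persistent rate is assumed to be 5%.

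| Assumed p0 | c, n=65 | P(flag) at true 5%, n=65 | c, n=73 | P(flag) at true 5%, n=73 | p for 4 of 65 | p for 4 of 73 |
|---|---|---|---|---|---|---|
| 0.3% | 2 | 84.2% | 2 | 88.5% | 0.00005 | 0.00007 |
| 1% | 3 | 63.7% | 3 | 71.3% | 0.0042 | 0.0063 |
| 2% | 4 | 41.0% | 5 | 30.1% | 0.041 | 0.059 |
| 3% | 5 | 22.5% | 6 | 15.8% | 0.131 | 0.176 |

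At a true rate of 3% with n = 65, the flag probabilities for p0 of 0.3%, 1% and 2% fall to 58.4%, 31.0% and 13.1%.

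**Step 5. Two illustrations of disagreement**
- *NOTE 2 followed.* The 6-month test flags the lens with the probabilities above. At 1 month the count in that category is 0, P(X ≥ 0) = 1, and the probability of flagging is 0 for every p0 (no sight-threatening cases assumed).
- *Any finding at 1 month counted.* Suppose 4 of 65 eyes (6.2%) have edema at 1 month and all clear before day 120. The 1-month test rejects at p0 of 0.3%, 1% and 2%; the 6-month count is 0 of 65, p = 1. This does not hold everywhere: 4 events do not reject at p0 = 3%, nor at 2% with 73 eyes.

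**The case against.** **The plan does name its primary test.** A reader might infer that the governing date is undefined. The documents do not support that. The 1-month test stands under the primary safety heading in both documents, 7.6 stands under the other endpoints, and both documents name 1 month as the key timeframe. This stands. What remains is a false cross-reference, which could also be meant to carry over the method into an additional 6-month test.

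**NOTE 2 defines seriousness, not the ISO count.** The endpoint is adverse event rates, and neither document says that NOTE 2 decides what is counted or that these persistent conditions are ISO-listed. This also stands, so this half of the point is conditional. It does not rescue the 1-month date: the protocol offers no other rule for persistence, and counting without one leads to the second illustration.

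**Nothing is lost.** It is tempting to read 84% against 0% as a loss of detection. It is not. The 6-month test is already in SAP 7.6, rates are reported over time, and SAP Appendix I plans findings at each visit and cumulatively. The contrast shows what the test labelled primary can do, not what the study can see.

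**Side evidence is weak.** Protocol 10.7 calls the 6-month visit the key exam for safety, but in a remark on capsulotomy timing that also names effectiveness, whose endpoint is at 1 month. As for retinal events, "A dilated fundus exam is to be performed at the 6-month visit to evaluate retinal status and fundus visualization", and no earlier postoperative one is scheduled. A reader might infer that such events cannot enter a 1-month count. Yet symptoms are asked about at every postoperative visit, and unscheduled visits may include a fundus exam, so symptomatic cases can be found sooner.

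**An early look is a fair choice** in a preliminary study. No section ties lens selection to the adverse-event test, and no safety success criterion is stated. That argues for letting the sponsor keep a 1-month look, provided its limits are written down.

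**Conclusion.** The point holds in two parts. The date conflict is certain: the same first-eye exact test is dated 1 month in SAP 6.1, 6.2 and Protocol 20.2, and 6 months in SAP 7.6, which wrongly attributes its date to 6.1 and 6.2. This rests on no assumption.

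The second part is conditional. If persistent edema, iritis and raised IOP are among the ISO-listed events and NOTE 2 classifies them, the primary test cannot assess those categories except for sight-threatening cases, because the first-eye windows are at least 30 days apart. All other listed events remain testable at 1 month. The flag probabilities and p-values are illustrations on assumed SPE and true rates.

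The change should be made: the labelled primary test and the 6-month test can give opposite answers, and everything needed to correct this is already planned.

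**What to change.** **Preferred.** In SAP 6.1, 6.2, 7.6 and Protocol 20.2, make the 6-month visit the date of the primary ISO SPE comparison, at least for the persistent categories. Count persistent corneal edema, iritis and raised IOP at the final visit under NOTE 2, and count the other listed events cumulatively through that visit. Keep the 1-month rates by lens group as a descriptive early look.

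**If 1 month must stay primary for lens selection.** State in SAP 6.1, 6.2 and Protocol 20.2 that persistent events are excluded from that test and are tested at 6 months under SAP 7.6. Reword 7.6 so that it refers to 6.1 and 6.2 for the method only, with its own date.

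**Cost.** Wording only. The 6-month visit, its exams and 65 evaluable subjects per group at that visit are already planned. The downside of the preferred option is delay: comparing like ends of the two windows, 120 - 30 = 90 days to 180 - 60 = 120 days, so the formal result for persistent events comes about 3 to 4 months after the 1-month effectiveness result.
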